If a patient on study undergoes successful surgical resection, the hydrogel injection sites between pancreas and duodenum will be examined for implant location and to identify any local inflammatory reactions.

b. Study duration and number of study visits required of research participants.

The TraceIT injection will be performed during the endoscopic fiducial placement which is the standard of care. Therefore, there will be no additional study visits needed by patients participating in this study.

c. Blinding, including justification for blinding or not blinding the trial, if applicable.

There is no blinding on this trial.

d. Justification of why participants will not receive routine care or will have current therapy stopped.

Patients will receive the standard of care treatment and will not have routine therapy stopped.

e. Justification for inclusion of a placebo or non-treatment group.

Date: 3/13/18

Principal Investigator: [name].

Application Number: IRB00151816

There is no placebo group in this trial.

f. Definition of treatment failure or participant removal criteria.

Patients will not be enrolled if the routine standard-of-care procedure of fiducial placement cannot be performed.

g. Description of what happens to participants receiving therapy when study ends or if a participant's participation in the study ends prematurely.

Patients will continue to receive the standard-of-care for their radiation therapy treatment.

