**2. Drugs/ Substances/ Devices**

- a. The rationale for choosing the drug and dose or for choosing the device to be used.

TraceIT Tissue Marker consists of an absorbable polyethylene glycol (PEG) hydrogel with covalently bound iodine (~1%). TraceIT Tissue Marker is indicated for use to radiographically mark soft tissue during a surgical procedure or for future surgical

Date: 3/13/18

Principal Investigator: [name].

Application Number: IRB00151816

procedures. TraceIT hydrogel is intended to mark tissue for at least 3 months after injection. TraceIT Tissue Marker is FDA approved for marking anywhere in the body, including the interface between duodenum and pancreas however this has not yet been attempted in clinical practice.

- b. Justification and safety information if FDA approved drugs will be administered for non-FDA approved indications or if doses or routes of administration or participant populations are changed.

N/a

- c. Justification and safety information if non-FDA approved drugs without an IND will be administered.

N/a

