### **3. Study Statistics**

- a. Primary outcome variable:

The success of injecting TraceIT using EUS for guidance will be assessed on post-injection simulation CT scan and determined as successful if TraceIT hydrogel is visible between the pancreatic tumor and duodenum on axial CT.

- b. Secondary outcome variables:

- 1) Visibility of TraceIT on daily cone beam CT acquired as standard of care for image-guided radiation therapy, defined as no visibility, poor visibility, or acceptable visibility by radiation oncologist.
- 2) For patients proceeding to surgical resection, the pathologic specimen will be analyzed grossly and on histopathologic specimen sections for TraceIT placement location and inflammation surrounding placement site.

- c. Statistical plan including sample size justification and interim data analysis.

No formal hypothesis or sample size estimation has been established since this is an early feasibility study with an intent to collect information concerning the procedural characteristics and safety for TraceIT administration within the peri-duodenal space. Six (6) subjects should provide sufficient experience to assess the success of the procedure to result in injecting of the hydrogel marker in the desired location.

No interim data analysis is planned

- d. Early stopping rules.

Date: 3/13/18

Principal Investigator: [name].

Application Number: IRB00151816

If TraceIT placement is unsuccessful as defined by the primary variable outcome in all of the first 3 patients, then the study will be terminated early as this would be an indication that revisions to the procedure would be necessary to facilitate success of the procedure.

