### **Potential Risk Associated with the TraceIT Hydrogel Material (RESEARCH)**

|                  |  |
|------------------|--|
| Likely           | 
 
• N/A
 
  |
| Less Likely      | 
 
• Minor bleeding
 
• Pain
 
   |
| Unlikely         | 
 
• Infection of the blood or other organs Clogging nearby blood vessels by the hydrogel material
 
• Inflammation of the pancreas or surrounding organs causing pain or discomfort
 
• Dislodgement of the TraceIT resulting in tracking to another site
 
• Improper placement of TraceIT into neighboring structures (e.g., duodenal wall)
 
• Foreign body reaction to TraceIT
 
• Delay in starting radiation therapy or surgery
 
 |
| Rare but serious | 
 
• Potential to worsen local progression of the cancer due to undiagnosed/microscopic invasion into the duodenum
 
  |

There may be side effects and discomforts that are not yet known.

b. Steps taken to minimize the risks:

The risks associated with EUS procedures and fiducial marker/TraceIT administration will be minimized via selection of experienced investigators who are skilled in EUS/transduodenal fiducial placement procedures. Additionally, participating gastroenterologist has prior experience with placement of the TraceIT hydrogel in human cadavers. Subjects will be selected and enrolled using clearly defined inclusion and exclusion criteria to ensure the best possible treatment outcome. Additionally, subjects will receive full and careful follow-up.

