The TraceIT hydrogel, is FDA cleared for use as a Tissue Marker and is specifically indicated for use to radiographically mark soft tissue during a surgical procedure or for future surgical procedures. The risks associated with the TraceIT hydrogel have been minimized by formulating the hydrogel with constituents that have a long history of safe use in implantable medical devices. The study sponsor conducted Biocompatibility testing in compliance with FDA's Good Laboratory Practices regulation and in accordance with ISO 10993 – Biological Evaluation of Medical Devices. Tests were selected and performed according to the type of device, intended use, and degree and duration of tissue contact. The response to TraceIT hydrogel was evaluated in healthy tissues including subcutaneous and intramuscular implant locations. All biocompatibility testing results are consistent with a biocompatible material.

Preclinical studies were also done to evaluate the response to TraceIT hydrogel when placed in the pancreatic parenchyma and duodenal wall. No adverse histologic change or safety concerns were noted.

Date: 3/13/18

Principal Investigator: [name].

Application Number: IRB00151816

Appropriate therapeutic intervention following standard medical practices will be used in the event of medical complications.

c. Plan for reporting unanticipated problems or study deviations:

The principal investigator will notify the appropriate regulatory agencies of any serious adverse event due to any cause during the course of this investigation. These include the Johns Hopkins Cancer Center Data and Safety Monitoring Committee, and the Johns Hopkins Medical Institutional Review Board (JHM-IRB) of The Johns Hopkins Medical Institutions. The required reporting time period is 3 days for fatal events, and 10 days for all other events.

d. Legal risks such as the risks that would be associated with breach of confidentiality:

While data will be stored in securely locked files (computer files will be password protected and any paper records will be stored in the research office at Johns Hopkins under lock and key) in which only the research team has access, there is always the risk that confidentiality will be lost.

e. Financial risks to the participants: None

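### The only stopping rule concerns failed placement; nothing makes the next TraceIT injection wait after a possibly related serious adverse event

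*Combined protocol and SAP*

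**What the plan says.** Study Statistics, item d, contains one rule: "If TraceIT placement is unsuccessful as defined by the primary variable outcome in all of the first 3 patients", the study stops, because the procedure would need revision. Item c plans no interim analysis, and gives as the study's intent to "collect information concerning the procedural characteristics and safety for TraceIT administration within the peri-duodenal space".

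The other places where a safety hold might stand are these:

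- Study Procedures, item f (treatment failure and removal), says only: "Patients will not be enrolled if the routine standard-of-care procedure of fiducial placement cannot be performed".
- Risks, item b, relies on experienced operators, the eligibility criteria and follow-up, and on treating complications by usual practice.
- Risks, item c, sets the reporting duty: "The principal investigator will notify the appropriate regulatory agencies of any serious adverse event due to any cause during the course of this investigation". The recipients include the Data and Safety Monitoring Committee and the IRB. On timing: "The required reporting time period is 3 days for fatal events, and 10 days for all other events".
- Study Procedures, item b, states that "there will be no additional study visits needed by patients participating in this study".

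The hydrogel risk table lists, as unlikely, blood infection, pancreatic inflammation and "Clogging nearby blood vessels by the hydrogel material". The Benefits section says that participants gain nothing from taking part. The Abstract says that this region has not been injected with the marker in humans before.

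**The concern.** The plan already accepts that early patients should decide whether later ones are injected, but it applies this only to placement. A serious event in an early patient, even a fatal one, triggers a report and treatment of that patient and nothing else. Until the report is due, the written plan lets the next scheduled patient be injected. That patient gets no benefit from the injection, at a site with no earlier human data, while the people able to judge the event may not know of it. Safety is part of the stated intent, so one would expect the stopping item to respond to harm as well as to failed placement.

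**Working it through.** **The text.** The sections listed above were checked for a second stopping rule, a hold after a serious event, staggered injections or a minimum interval between patients. None has one. The plan states no figure on this point, so there is none to reproduce.

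**The existing rule does not see harm.** With placement success rate s, it fires with probability (1 − s)³. At the swine rate in Background, 6/8 = 0.75, that is 0.25³ = 1.6%. Safety does not enter the formula.

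**Chance of exposure.** Inputs from the documents: 6 patients, so an event in patients 1 to 5 leaves at least one injection to come; window w = 10 days for non-fatal events. Assumed, because the documents give neither: related serious-event rate p per patient of 1%, 2% or 5%; injection rate r of 0.5, 1 or 2 per month of 30.4 days, with Poisson arrivals. Also assumed: the event occurs at injection, and the full window is used.

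- Chance of another injection within w days: q = 1 − exp(−w·r/30.4). For w = 10: 0.152, 0.280 and 0.482 at r = 0.5, 1 and 2.
- Chance that, for at least one of patients 1 to 5, an event is followed by an injection inside the window: 1 − (1 − p·q)⁵.

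| p | r = 0.5 | r = 1 | r = 2 |
|---|---|---|---|
| 1% | 0.8% | 1.4% | 2.4% |
| 2% | 1.5% | 2.8% | 4.7% |
| 5% | 3.7% | 6.8% | 11.5% |

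If reports take 5 days, the range at p = 1% to 2% falls to 0.4% to 2.8%.

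**From exposure to injury.** If the next patient's risk is the same p, and at most one injection falls in the window, multiply by p. This gives 0.0076 × 0.01 = 0.008% at the low end and 0.1148 × 0.05 = 0.6% at the high end. This treats the first event as uninformative. The reason for a hold is that an event may show the true risk to be higher than thought, and the documents give no basis for quantifying that.

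**Holds caused by the fiducials.** TraceIT and fiducials are placed in one session, and both risk tables list pancreatic inflammation and blood infection. At an assumed 1% to 2% serious-event rate from fiducial placement alone, the chance of at least one such hold over patients 1 to 5 is 1 − (1 − p)⁵ = 4.9% to 9.6%. This counts every hold whether or not a patient is due, so it cannot be set directly against the exposure figures.

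**What a hold cannot catch.** If an event surfaces d days after injection, the chance that the next patient has already been injected is 1 − exp(−d·r/30.4). At r = 0.5 to 2 this is 5% to 18% for d = 3 and 11% to 37% for d = 7.

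**The case against.** The best defence is that the absolute risk is small and oversight exists. Drugs/ Substances/ Devices, item a, says that "TraceIT Tissue Marker is FDA approved for marking anywhere in the body, including the interface between duodenum and pancreas". The volume is 0.3 to 1.0 mL per site. Deliberate mis-injection in swine caused neither pancreatitis nor duodenal necrosis. The marker has been used in esophagus, bladder and cervix, and the gastroenterologist has placed it in cadavers. Every serious event goes to a standing committee and the IRB, 10 days is a maximum, follow-up is promised, and the planning CT falls within 10 days of placement. A single-site investigator would probably pause anyway, and institutional rules outside these documents may require it. All of this stands and keeps the severity low. It does not put a hold in the protocol, and the committee can act only once told.

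A second objection concerns the cost of a hold. Because TraceIT is given during the fiducial session and no extra visits are planned, a patient whose session falls in a hold misses TraceIT; it is not merely delayed. Postponing the session instead would bring on a delay in radiation, which the risk table already lists. This is correct, and the fix has to provide for it.

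A reader might infer that the trial lacks safety oversight or uses the marker outside its approval. The reporting duty and the device section contradict both. A reader might also take the label for unlikely risks to mean 1% to 2%. The risk tables attach no percentages to any label, so every rate used here is an assumption.

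**Conclusion.** The gap is real and of low severity. The only early stopping rule concerns failed placement, and no section makes the next TraceIT injection wait after a possibly related serious event. Another patient could therefore be injected before the committee is told, up to 3 days after a fatal event or 10 days after any other.

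The size depends entirely on assumed event and accrual rates: 0.8% to 11.5% over the grid above, less if reports are prompt. It is tempting to read this as a chance of harm, but it is only the chance that a further patient is exposed inside the window. Whether institutional rules already close the gap cannot be judged from these documents.

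**What to change.** Add to Study Statistics, item d:

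> After any serious adverse event judged at least possibly related to the TraceIT injection, including any that cannot be separated from the same-session fiducial placement, no further patient will receive TraceIT until the event has been reported to the Data and Safety Monitoring Committee and the committee has agreed to resume. Standard-of-care fiducial placement and SBRT will not be postponed for a hold. A patient whose fiducial session falls within a hold will not receive TraceIT and will not count toward the six; the slot will pass to a later patient.

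The 3-day and 10-day limits can stay. The number of injected patients stays at six, and no visit or procedure is added. Because Study Procedures speaks of six enrolled, the wording there should allow for a replaced patient.

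The cost is slower accrual if a hold occurs, including holds that turn out to be due to the fiducials. The committee must also answer on restart, and the documents do not say how quickly it would. The hold does nothing for events that surface after the next injection.

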#### 4. Risks

- a. Medical risks, listing all procedures, their major and minor risks and expected frequency.
- b. Steps taken to minimize the risks.
- c. Plan for reporting unanticipated problems or study deviations.
- d. Legal risks such as the risks that would be associated with breach of confidentiality.
- e. Financial risks to the participants.

a. Medical risks associated with the study procedures can be divided into those associated with the EUS procedure for fiducial/TraceIT hydrogel administration and potential risks associated with the hydrogel.

#### **Potential Risk Associated with the EUS Procedure and Fiducial Placement (STANDARD OF CARE)**

|                  |   |
|------------------|---|
| Likely           | 

• N/A

   |
| Less Likely      | 

• Minor bleeding

• Pain

• Melena (blood in the stool)

   |
| Unlikely         | 

• Fever/Infection

• Major bleeding due to damage to blood vessels

• Nerve damage

• Inflammation of the pancreas

• Temporary issues with breathing or infection to the lung as a result of improper swallowing

• Side-effects or complications related to anesthesia (temporary low blood pressure and worsening of pre-existing heart or lung problems)

• Improper placement or migration of the fiducial implant

• Foreign body reaction to fiducial

 |
| Rare but serious | 

• Difficulty breathing or death due to anesthesia

• Unintentional perforation of organs not intentionally involved in the procedure

• Spread of the cancer to nearby tissues as a result of spillage caused by the procedure

• Infection of the blood or other organs

• Death

   |

### **Potential Risk Associated with the TraceIT Hydrogel Material (RESEARCH)**

|                  |  |
|------------------|--|
| Likely           | 
 
• N/A
 
  |
| Less Likely      | 
 
• Minor bleeding
 
• Pain
 
   |
| Unlikely         | 
 
• Infection of the blood or other organs Clogging nearby blood vessels by the hydrogel material
 
• Inflammation of the pancreas or surrounding organs causing pain or discomfort
 
• Dislodgement of the TraceIT resulting in tracking to another site
 
• Improper placement of TraceIT into neighboring structures (e.g., duodenal wall)
 
• Foreign body reaction to TraceIT
 
• Delay in starting radiation therapy or surgery
 
 |
| Rare but serious | 
 
• Potential to worsen local progression of the cancer due to undiagnosed/microscopic invasion into the duodenum
 
  |

There may be side effects and discomforts that are not yet known.

b. Steps taken to minimize the risks:

The risks associated with EUS procedures and fiducial marker/TraceIT administration will be minimized via selection of experienced investigators who are skilled in EUS/transduodenal fiducial placement procedures. Additionally, participating gastroenterologist has prior experience with placement of the TraceIT hydrogel in human cadavers. Subjects will be selected and enrolled using clearly defined inclusion and exclusion criteria to ensure the best possible treatment outcome. Additionally, subjects will receive full and careful follow-up.

The TraceIT hydrogel, is FDA cleared for use as a Tissue Marker and is specifically indicated for use to radiographically mark soft tissue during a surgical procedure or for future surgical procedures. The risks associated with the TraceIT hydrogel have been minimized by formulating the hydrogel with constituents that have a long history of safe use in implantable medical devices. The study sponsor conducted Biocompatibility testing in compliance with FDA's Good Laboratory Practices regulation and in accordance with ISO 10993 – Biological Evaluation of Medical Devices. Tests were selected and performed according to the type of device, intended use, and degree and duration of tissue contact. The response to TraceIT hydrogel was evaluated in healthy tissues including subcutaneous and intramuscular implant locations. All biocompatibility testing results are consistent with a biocompatible material.

Preclinical studies were also done to evaluate the response to TraceIT hydrogel when placed in the pancreatic parenchyma and duodenal wall. No adverse histologic change or safety concerns were noted.

Date: 3/13/18

Principal Investigator: [name].

Application Number: IRB00151816

Appropriate therapeutic intervention following standard medical practices will be used in the event of medical complications.

c. Plan for reporting unanticipated problems or study deviations:

The principal investigator will notify the appropriate regulatory agencies of any serious adverse event due to any cause during the course of this investigation. These include the Johns Hopkins Cancer Center Data and Safety Monitoring Committee, and the Johns Hopkins Medical Institutional Review Board (JHM-IRB) of The Johns Hopkins Medical Institutions. The required reporting time period is 3 days for fatal events, and 10 days for all other events.

d. Legal risks such as the risks that would be associated with breach of confidentiality:

While data will be stored in securely locked files (computer files will be password protected and any paper records will be stored in the research office at Johns Hopkins under lock and key) in which only the research team has access, there is always the risk that confidentiality will be lost.

e. Financial risks to the participants: None

**5. Benefits**

a. Description of the probable benefits for the participant and for society:

The tissue interface between pancreas and duodenum can be potentially marked using this radiopaque hydrogel. There is no benefit to the patient from participation in the study. Potential benefits to society include those to future patients undergoing SBRT treatments, who may receive improved treatment as a direct result of the research performed in this study. If this procedure is determined to be feasible in this study, future investigations will be planned to use the hydrogel to increase the distance between the pancreas and duodenum in the region of the pancreatic tumor to serve as a physical spacer so that the duodenum can be displaced away from the higher dose region.

**6. Payment and Remuneration**

a. Detail compensation for participants including possible total compensation, proposed bonus, and any proposed reductions or penalties for not completing the protocol:

There will be no compensation for participants.

**7. Costs**

a. Detail costs of study procedure(s) or drug (s) or substance(s) to participants and identify who will pay for them:

Augmenix will provide the device (TraceIT Tissue Marker) and a separate FNA needle for injecting TraceIT.

